4.2.2 Secondary and Exploratory Outcome Variables (if applicable)

From the intervention and control groups, we will gather data on in-hospital outcomes of importance to older adults, including but not limited to delirium, mobility level, muscle strength at discharge, functional status at discharge, and ICU/hospital lengths of stay. We will also submit a JDAT request for deidentified, aggregate historical data from the York Street MICU on the same in-hospital outcomes.

From the intervention and control groups, at approximately 30 days after hospital discharge, we will also gather data on functional outcomes, cognitive outcomes, and health outcomes (including, but not limited to, readmissions). From the intervention group only, we will gather feedback and data about ongoing use of the portable amplifying device since hospital discharge.

4.3 Study Population

This is a prospective pilot study that will draw participants aged 65 and older from the 36-bed medical intensive care unit (MICU) of the main campus of Yale-New Haven Hospital (YNHH). All patients aged ≥ 65 who are admitted to the MICU will be screened for enrollment.

Nursing providers, occupational therapists, and ICU pharmacists delivering the bundle components will also be enrolled as study participants (“provider participants”).

4.3.1 Number of Participants

We plan to enroll 80 patient participants (30 in the control group, and 50 in the intervention group). Of the providers, we plan to enroll 75 nurses and all of the occupational therapists and ICU pharmacists (approximately 3-5 in each group) who deliver the interventions.

4.3.2 Eligibility Criteria/Vulnerable Populations

This is a prospective pilot study that will draw participants from the 36-bed medical intensive care unit (MICU) of the main campus of Yale-New Haven Hospital (YNHH), where approximately half of the 2900 annual admissions are among patients age 65 and older. All patients age 65 and older who are admitted to the YNHH MICU will be screened for enrollment. Inclusion and exclusion criteria for the patient participants are outlined in the table below.

For the provider participants, all nurses, occupational therapists, and ICU pharmacists delivering the bundle components will be eligible for inclusion. The only exclusion criterion for the nurses is if the nurse encountered by the research team is not the patient’s primary nurse (such as if the nurse is covering for the primary nurse’s lunch break).

Table 1. Inclusion and Exclusion Criteria

Inclusion Criteria	Exclusion Criteria
1. Age ≥ 65 years	1. Unable to provide informed consent and no proxy available

2. Hospitalized in the Medical Intensive Care Unit (MICU) on the York Street campus of Yale-New Haven Hospital.
 
3. Has not opted out of research
	
2. Advance directive of "comfort measures only" (CMO) or change to CMO anticipated during this hospital admission
 
3. Planned discharge to hospice
 
4. Primary language other than English
 
5. Tracheostomy with long-term ventilator dependence
 
6. Patients with non-family conservators (e.g. a lawyer serving as the conservator for the patient)
 
7. Unable to participate in the OT and hearing impairment interventions due to cognitive status (e.g. advanced dementia, anoxic brain injury, vegetative state, etc) or the need for deep sedation (e.g. if treatment of the critical illness requires deep sedation and neuromuscular blockade, such as in severe ARDS [the acute respiratory distress syndrome])
 
8. COVID-19 positive
 
9. Already receiving OT in the ICU

--	--

5 Study Methods/Procedures

5.1 Study Procedures

Screening and enrollment of patients

The Yale-New Haven Hospital (YNHH) Joint Data Analytics Team (JDAT) will provide a list of medical intensive care unit (MICU) patients age 65 and older who have not opted out of research. Study personnel will review this list on a daily basis to screen for eligible patients. For screened patients, basic demographic information will be captured in a REDCap screening form as this is a feasibility study and we will need to provide descriptive statistics for the patients screened and enrolled. Study personnel will apply the inclusion and exclusion criteria from Table 1 (above in section 4.3.2) and identify eligible patients.

Once an eligible patient is identified, a research nurse or research assistant will assess the patient for his/her ability to consent and participate in the study interventions by first assessing mental status via the Richmond Agitation-Sedation Scale (RASS). For patients who are too deeply sedated (RASS -2 to -5) or agitated (+2 to +5), as often occurs in the ICU due to severity of illness or the need for mechanical ventilation, a proxy will be approached for consent. Patients with an acceptable RASS score (-1, 0, or +1) will undergo an assessment of delirium using the Confusion Assessment Method for ICU (CAM-ICU). For patients who are delirious according to the CAM-ICU, as often occurs in the ICU due to severity of illness, a proxy will be approached for consent. Patients who have acceptable RASS scores and a negative CAM-ICU will be approached for enrollment. If study personnel have any concerns about the patient's capacity to consent once they begin speaking to the patient, they will administer the University of California San Diego Brief Assessment of Capacity to Consent (UBACC). If the patient is found to lack decisional capacity, a proxy will be approached for consent.

Participants will be provided with a copy of the consent form. Proxies who sign the consent form in person will also be provided with a copy of the consent form. In light of hospital visitation restrictions due to COVID-19, and considering that many proxies will not want to visit the hospital during the COVID-19 pandemic, we will allow for verbal consent by proxy. If verbal consent by proxy is obtained, we will log this in the REDCap database and mail the proxy a key information sheet. The consent form will be signed by research personnel and scanned into REDCap. The research nurse will be required to check the following attestation in REDCap: "I verbally explained the purpose, procedures, risks, benefits, confidentiality, and voluntary nature of the ACE-ICU study. The proxy was given time to ask any questions and agreed to have the participant take part in the study."

Baseline interview and provision of portable amplifying device (45 minutes of participant contact)

After consent is obtained, the research nurse will perform a baseline interview that includes an assessment of geriatric factors, demographics, and in-hospital factors that have been found to be important in prior research. This interview is expected to take approximately 45 minutes. Data will be collected about demographics, health conditions, pre-ICU functional status, healthcare utilization, frailty, falls, social support, living situation, depressive symptoms, cognitive function, hearing impairment, and vision impairment. Hearing impairment will be assessed with the single-item hearing question in the National Health and Nutrition Assessment Survey (NHANES), which asks the participant or proxy to best describe the participant's hearing without a hearing aid or other listening device.

For participants enrolled during the intervention phase of the study, research personnel will then orient the participant and the nurse to the portable amplifying device and help set up the amplifier for the patient. A bedside laminated sheet with instructions on how to use the device will be provided and left at the bedside so that the participant and nurse have a resource for reference. Due to COVID-19 restrictions, every study participant will be provided with their own portable amplifying device which will be theirs to take home. Study personnel will then notify the physician team and occupational therapist of the participant's enrollment in the study, so that an OT order is placed in the EMR. The ICU pharmacy team will also be notified of the participant's enrollment.

Daily in-hospital audit (5 minutes of participant contact/day)

For participants enrolled during the intervention phase of the study, study personnel will perform a daily audit of use of the portable amplifying device. Participants will be asked a short series of questions about their device use. Study personnel will also ask the nurse about use of the device and will check the bedside log of device use.

Occupational therapy

For participants enrolled during the intervention phase of the study, the occupational therapist will assess the patient's need for OT and develop a treatment plan as they normally would in clinical practice. This study does not alter any aspect of the OT assessment or treatment plan; the study only ensures that OT is ordered as a default for all enrolled participants.

Deprescribing of potentially inappropriate medications (PIMs) started in the ICU

When a participant in the intervention arm is ready for transfer to the floor (as indicated by the primary MICU team placing a transfer order or indicating that they will place a transfer order that day), the ICU pharmacy team will review the active medication list for PIMs that were started in the ICU and are now potentially inappropriate. Common examples include atypical antipsychotics (often inappropriately started for ICU delirium) and acid suppressants (which are indicated for stress ulcer prophylaxis during mechanical ventilation, but are no longer indicated after discharge unless they are a home medication). The ICU pharmacist

will review the patient's home medication list to ensure that PIMs flagged for discontinuation were started in the ICU. The ICU pharmacist will then write a brief note in the EMR documenting which PIMs were discontinued and why.

Hospital discharge interview (45 minutes of participant contact)

Prior to hospital discharge, all participants will undergo an assessment of functional status, cognitive status (with the Montreal Cognitive Assessment), and 3 objective assessments: manual muscle testing according to the 6-point Medical Research Council (MRC) system,²⁷ hand grip dynamometry, and a short walk test. We will also ask participants in the intervention arm about perceived benefit of the portable amplifying device, their comfort with the device, and acceptability of the device.

- Manual muscle testing via the 6-point MRC system: Strength in each of 12 muscle groups is assessed via a 6-point system, in which a score of 0=no contraction, 1=flicker of a contraction, 2=active movement with gravity eliminated, 3=active movement against gravity, 4=active movement against gravity and resistance, 5=normal power.

30-day interview (15 minutes of participant contact)

At approximately 30 days after hospital discharge, we will call all participants (or their proxies) to ask about functional status, cognitive status, and health events (such as, but not limited to, readmissions). We will also ask participants in the intervention arm about ongoing use of the portable amplifying device since discharge.

Medical record abstraction

Study personnel will review the EMRs of all participants to gather data about the patient's demographics, health conditions, and clinical course in the hospital including, but not limited to, medications, ICU and hospital diagnoses, hospital length of stay, delirium, physical therapy treatments, SOFA score (a measure of severity of illness), as well as ICU treatments and complications (e.g. mechanical ventilation, tethering devices (e.g. lines, tubes, and restraints), and the need for dialysis). After the follow-up phone interview (or, if the patient cannot be reached, after the window for that follow-up interview has closed), study personnel will again review the EMR to capture data on health outcomes such as readmissions and mortality.

Payment for study participation

All participants will be given a \$50 gift card at the conclusion of study activities to thank them for participation in the study. In most cases, the gift card will be mailed to the participant after completion of the follow-up interview. If there are any concerns about the participant's ability to reliably receive the gift card after discharge (such as if the participant is being discharged to a short-term rehab facility), we will provide the gift card prior to hospital discharge.

Screening and enrollment of provider participants

Occupational therapy providers

At least one occupational therapist (OT) is assigned to the Medical Intensive Care Unit (MICU) as part of the quarterly rotation for rehab personnel who staff the MICU's STEPS-ICU early mobilization program. Research personnel will identify the occupational therapist(s) rotating through the MICU during the study period and approach them for inclusion in the survey and focus groups. The appropriate information sheet (survey only or survey and focus group) will be provided. We estimate that up to 5 occupational therapists will be enrolled in this study.

ICU pharmacist providers

There are three ICU pharmacists who are dedicated to the MICU. Research personnel will approach the three ICU pharmacists for inclusion in the survey and focus groups. The appropriate information sheet will be provided.

Nursing providers

Research personnel will identify the patient's primary nurse by reviewing the electronic medical record, including the patient's primary team in Mobile Heartbeat. Nurses in the ICU or who are caring for the patient on the ward (after ICU transfer) may be approached for inclusion in the survey and focus groups. The appropriate information sheet will be provided.

Payment for study participation

Focus group participants will be provided with a \$50 gift card at the conclusion of study activities to thank them for their participation. Survey respondents will not be compensated.

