4.2 Outcome Variables

4.2.1 Primary Outcome Variables

The primary outcomes are all implementation outcomes; therefore, they will only be evaluated among participants and providers enrolled during the intervention phase of the study. To evaluate the feasibility of bundle delivery in the ICU (SA1), we will assess the delivery of each bundle component separately. For the occupational therapy intervention (*Component 1*), we will review the electronic medical record (EMR) for OT notes from study enrollment through hospital discharge. In addition to gathering data on numbers of patients receiving OT, we will gather data about the frequency of and which OT interventions are performed. For the hearing impairment intervention (*Component 2*), we will perform a daily audit of use of the portable amplifying device. The daily audit will include asking the participant and nurse about use of the device, as well as checking a daily bedside log where use of the device is recorded. For the deprescribing intervention (*Component 3*), we will review the chart for the ICU pharmacist’s note. We will also gather data on the details of the deprescribing intervention (i.e. the number and type of medications that were changed or discontinued) as preliminary data for future studies.

To evaluate the acceptability of the geriatrics bundle among providers who are responsible for delivering and using the individual components (SA2), we will administer a survey with a 5-point Likert scale (range 1-5, where 5 indicates that the bundle is completely acceptable for use in its current form) to the providers who are responsible for delivering the intervention: occupational therapists (OT; *Component 1*), nurses (primarily, but also other ICU providers such as physicians and physical therapists; *Component 2*), and ICU pharmacists (*Component 3*).

To evaluate facilitators and barriers to implementation of the geriatrics bundle (SA3), we will use qualitative methods to allow for a more comprehensive understanding of barriers and

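### Length of stay, delirium and mobility have no stated time origin, although patients may be enrolled on any ICU day and the bundle starts only after enrolment

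*Combined protocol and SAP*

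**What the plan says.** Section 4.2.2 states: "From the intervention and control groups, we will gather data on in-hospital outcomes of importance to older adults". Its list includes delirium, mobility level, and "muscle strength at discharge, functional status at discharge, and ICU/hospital lengths of stay". The same section plans an aggregate historical extract from the same unit on the same in-hospital outcomes. Section 5.1 (Medical record abstraction) covers "clinical course in the hospital including, but not limited to, medications, ICU and hospital diagnoses, hospital length of stay, delirium, physical therapy treatments". No start point is given in either place.

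The inclusion criterion on location in Table 1 is "Hospitalized in the Medical Intensive Care Unit (MICU) on the York Street campus of Yale-New Haven Hospital", and on screening Section 5.1 says "Study personnel will review this list on a daily basis to screen for eligible patients". No criterion limits the ICU day. The nearest to one is exclusion 9, "Already receiving OT in the ICU", which sets no day limit.

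In Section 5.1 the amplifier and the OT order follow consent and the baseline interview ("the study only ensures that OT is ordered as a default for all enrolled participants"), and deprescribing comes at transfer to the floor. The OT feasibility measure does have an origin: Section 4.2.1 will "review the electronic medical record (EMR) for OT notes from study enrollment through hospital discharge".

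**The concern.** Days before enrolment cannot be changed by the bundle. They are also days the patient had to spend in hospital to be available for enrolment, so later enrolment selects longer stayers. In a randomised trial this would balance on average. Here 30 controls are enrolled first and 50 intervention patients afterwards, so a change in enrolment speed between phases would enter the comparison directly.

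The comparison matters because the primary outcomes use the intervention phase only (Section 4.2.1). The controls therefore contribute mainly through these secondary outcomes, which are to serve as preliminary data for a larger grant application. Section 5.4.4 allows bivariate and adjusted methods but names no covariate for enrolment timing.

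Delirium has a related problem. The synopsis speaks of its incidence, yet Section 5.1 enrols patients who are already delirious, through a proxy.

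**Working it through.** The documents give no expected stay, SD or time to enrolment, so there is no figure of the plan's own to reproduce. Only the group sizes (30 and 50) come from the protocol. Every other input below is an assumption.

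**1. Shift with no bundle effect (simulation).** ICU stay is lognormal with median 4 days and log-SD 0.6, 0.8 or 1.0. Ward stay is lognormal with median 5 days and log-SD 0.7. The offer of enrolment comes at an exponential time with mean 1 to 4 days from ICU admission, and a patient is enrolled only if still in the ICU. Four control v intervention pairs of mean offer time were run (1 v 2, 1 v 3, 2 v 3 and 2 v 4 days). Hospital days before ICU admission are not modelled.

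Before enrolment fall 6% to 17% of hospital days and 12% to 36% of ICU days. Over the four pairs, a gap of 0.34 to 1.08 days in mean time to enrolment gives:
- whole stay: +0.22 to +1.30 days, longer in the later-enrolled phase;
- stay from enrolment: -0.38 to +0.26 days.

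For the widest pair (1 v 3 days), with a two-sided 5% Wilcoxon test, 30 v 50 patients and 3,000 replicates:

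| ICU log-SD | Gap before enrolment (days) | Whole-stay difference (days) | Post-enrolment difference (days) | False positives, whole stay | False positives, from enrolment |
|---|---|---|---|---|---|
| 0.6 | 0.88 | +0.50 | -0.38 | 6.6% | 6.4% |
| 0.8 | 0.98 | +0.88 | -0.11 | 9.0% | 4.8% |
| 1.0 | 1.08 | +1.30 | +0.22 | 10.6% | 5.1% |

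With equal timing (1 v 1 day) the whole-stay rates were 3.9%, 5.8% and 5.2%. Simulation error near 5% is √(0.05 × 0.95 / 3000) = 0.4 points.

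The whole-stay difference equals the gap plus the post-enrolment difference: 0.88 - 0.38 = 0.50 and 1.08 + 0.22 = 1.30. The gap therefore does not carry over one for one, because later enrolment changes who is enrolled. It also follows that resetting the clock is not enough alone. At log-SD 0.6 the bias changes sign and the error rate hardly moves.

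**2. Size against what the study could detect.** The difference detectable with 80% power at two-sided 5% is (1.960 + 0.842) × SD × √(1/30 + 1/50) = 0.647 × SD. That is 3.9 days for SD 6 and 7.8 days for SD 12. In the 1 v 3 pair, the SD of whole stay is about 6.0 to 6.1 at log-SD 0.6, so a shift of 0.50 sits against about 3.9 days. At log-SD 1.0 the SD is 10.3 to 11.0, so a shift of 1.30 sits against 6.7 to 7.1 days. By the same normal calculation, a pure artefact of 1 day would reach p < 0.05 with probability 0.108 + 0.004 = 11.2% at SD 6 and 0.055 + 0.010 = 6.5% at SD 12.

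**3. Delirium.** Suppose new delirium after enrolment is 40% in controls and 25% with the bundle, and a fraction q is already delirious at enrolment. Counting any in-hospital delirium gives q + (1 - q) × 0.40 against q + (1 - q) × 0.25, a difference of (1 - q) × 15 points. For q = 20%, 40% and 60% this is 12, 9 and 6 points. Power with 30 v 50 falls from 29% to 18%, 12% and 8%.

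**The case against.** The strongest reply is that nothing here is a stated error. Section 5.1 lists data to abstract and does not define an analysis window, so abstracting the full course does not prevent counting from enrolment later. The secondary objective (Section 3.3) is descriptive, no test of stay by phase is specified, and Section 5.4.4 already speaks of adjustment and the limits of observational data. Screening and consent are described once for both phases. Verbal proxy consent (Sections 5.1 and 5.3.2) shortens the delay that visitor restrictions would cause. Sedated patients can enter through a proxy, although exclusion 7 could still hold back some who need deep sedation.

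Much of this stands. A reader might infer that the plan fixes a whole-stay window, or that a spurious effect is to be expected. The documents support neither: the window is only the natural reading, and nothing shows that timing will differ. A difference is possible, because Version 4 removed the witness requirement for proxy consent and added roster review to screening, but no enrolment dates show which phase this reached. The direction is open too. Later enrolment in the intervention phase would make the bundle look worse on whole stay, and earlier enrolment would make it look better.

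A reader might also extend the point to every abstracted item. Section 4.2.2 does not name physical therapy treatments, ventilation or tethering devices as outcomes, and these, with SOFA and diagnoses, may properly describe the full stay.

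The descriptive label does not remove the point. Side-by-side summaries of two sequential groups will be read as a comparison, and the plan does not ask for the one variable that would show whether enrolment timing explains a difference.

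**Conclusion.** The point holds for ICU and hospital stay, delirium and mobility: the time origin is undefined, and the ordinary reading counts days that precede the bundle. If time to enrolment differs by phase, the simulated shift in hospital stay is about 0.2 to 1.3 days. This rests wholly on the assumed stay and offer-time distributions and on an assumed gap. A shift of that size would mostly move the preliminary estimate; in the widest pair the false-positive rate was 6.6% to 10.6%. Primary outcomes, strength, function and cognition at discharge, SOFA, diagnoses and descriptive ICU treatment data are unaffected. This is a cheap improvement to secondary outcomes and does not bear on the main aims or the sample size.

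**What to change.** In Sections 4.2.2, 5.1 and 5.4.4, for any summary that sets control against intervention:

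- Count ICU stay, hospital stay and mobility from the date of enrolment.
- Separate delirium present at enrolment from new delirium. The CAM-ICU at consent supplies the status where it was done. Patients enrolled by proxy on RASS alone need a stated rule, such as chart status or not assessable.
- Record ICU and hospital days before enrolment, report them by phase, and include them as a covariate. Patients enrolled on the same ICU day have all remained in the ICU to that day, so this addresses the selection that the clock change leaves.
- Keep admission-to-discharge stay as a secondary line for comparison with the aggregate historical data.

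The cost is analysis wording. Admission, transfer and discharge dates should already be in the medical record, and no extra patient contact is needed. The one drawback is that stay from enrolment cannot be compared directly with the historical extract, which is why the admission-based figure is kept.
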